# 4.11 Analysis plan

Primary analyses compare the BP and plasma lipid concentrations measured at the end of the CARB diet with those at the end of the PROTEIN and UNSAT diets, within each individual among all participants.

*Outcome definitions*. For **Specific Aim 1**, the primary outcome is constructed as follows. The SBP measure associated with a given diet is the mean of the five SBP measures obtained in the final two weeks of the intervention period for that diet. The primary outcome for each participant for the PROTEIN diet is the difference between the participant's SBP measure for that diet and the corresponding SBP measure for the CARB diet. The primary outcome for each participant for the UNSAT diet is the difference between the participant's SBP measure for that diet and the corresponding SBP measure for the CARB diet. The secondary outcome for Specific Aim 1 is constructed analogously using DBP instead of SBP measures. For **Specific Aim 2**, the lipid values associated with a given diet are obtained from the week 6 fasting blood sample for that diet. The primary lipid outcome for each participant for the PROTEIN diet is the difference between the participant's LDL-C from that diet and his/her corresponding LDL-C measure from the CARB diet. The primary outcome for each participant for the UNSAT diet is the difference between the participant's LDL-C from that diet and his/her corresponding LDL-C measure from the CARB diet. The primary outcome for each participant for the UNSAT diet is the difference between the participant's LDL-C for that diet and his/her corresponding LDL-C measure from the CARB diet. The primary outcome for each participant for the UNSAT diet is the difference between the participant's LDL-C for that diet and his/her corresponding LDL-C measure from the CARB diet. The primary outcome for each participant for the CARB diet. Other lipid outcomes in **Specific Aim 2** and all outcomes for **Specific Aims 3 and 4** are derived in like fashion for each of the components identified in the statement of the relevant Specific Aim.

*Analysis framework.* The inferences of interest concern efficacy of the proposed diets in reducing risk of cardiovascular disease. All pairwise comparisons between diets will be evaluated for all outcomes. Primary analyses will be conducted on a per protocol basis, excluding information on study dropouts whenever incompleteness interferes with a given comparison, i.e., an individual who completes only two diets contributes information to only one comparison. Primary analyses will be supplemented by detailed information on dropouts, and by analysis of sensitivity of inferences to the occurrence of dropouts. These secondary analyses will investigate patterns of missingness, will attempt to discern if missingness is associated with features of the response profile, and will employ multiple imputation from the posterior predictive distribution of the outcome on the opposing arm to obtain a conservative secondary inference. The standard multiple imputation variance (Rubin, 1987) will be used to obtain secondary test statistics and confidence intervals. In the previous DASH trials, such incompleteness was very rare.

Inferential contrasts will be calculated using the simplest appropriate statistical method. For example, with the SBP outcome, the equal-variances paired t-test of equal blood-pressure effects on two diets will likely be satisfactory. Ninety-five (95) percent confidence intervals will be reported for the effects of PROTEIN and UNSAT relative to CARB. The effect of PROTEIN compared to UNSAT will be reported, but this pairwise contrast is not independent of the other 2 primary comparisons. Supplementary detailed modeling of the trajectory of repeatedly observed outcomes and its dependence on covariates will be conducted in the mixed effects models framework (Laird and Ware, 1982).

*Multiple comparisons*. Statistical significance will be reported without adjustment for multiple comparisons, and all point estimates and p-values will be accompanied by unadjusted 95% confidence intervals for the mean difference. For each analysis, statistical significance will be defined by p (unadjusted) <0.05.

*Subgroup analyses*. Analyses will be performed separately within subgroups. Pre-specified subgroups of interest are those defined by gender (women, men), race-ethnicity (African-Americans, non-African-Americans), menopausal status (pre-menopausal women, post-menopausal women), age, weight status, and baseline level of the outcome variable. Subgroups analyses defined by other pre-randomization variables may also be conducted, but these analyses will be reported as exploratory.

In general, prevailing national recommendations (e.g. JNC and ATP) guide selection of cut-points for subgroup-defining variables with a continuous distribution. Hypertension is defined by baseline SBP  $\geq$  140 mmHg and/or DBP  $\geq$  90 mmHg, and non-hypertension by baseline SBP < 140 mmHg and DBP < 90 mmHg. Other prospectively defined cutpoints are as follows: LDL cholesterol (130 mg/dl, 160 mg/dl), HDL cholesterol [40 mg/dl (all), 40 mg/dl (men), 50 mg/dl (women)], triglycerides (150 mg/dl), baseline weight [non-overweight (BMI < 25 kg/m^2), overweight (25 kg/m^2  $\leq$  BMI < 30 kg/m^2), obese (BMI  $\geq$  30 kg/m^2)]. The cutpoint for age is the median (above median age, below median age). For continuous subgroup-defining factors such as age, baseline BP, and baseline lipids, more powerful inferences may be achieved using continuous formulations of the predictor in analysis of covariance. Also, in some cases, the dispersion in a factor of interest may require a non-prespecified stratification definition, or introduction of a sophisticated analysis tool such as spline regression. Such analyses will be reported as exploratory.

*Kinetic modeling*. Kinetic modeling of outcomes are used to assess whether a steady state has been achieved. To this end, we also employ mixed effects models. The 6 week duration of the feeding perio makes it feasible to fit detailed models of outcome trajectories. These outcomes include BPs measured weekly during each intervention period and laboratory measurements measured during weeks 4 and 6 of each period. A standard tool is the nonlinear mixed effects model (Pinheiro 2000). For intensively monitored outcomes such as BP components, it is anticipated that asymptotic regressions, that is, of the form mean  $Y = a + (b-a)exp(-c^{*t})$ , where a is final level, b is initial level, and c is a rate constant, can be fit at the individual level. For lipids, glucose and insulin, which are sampled at weeks 4 and 6, inference on variance components corresponding to subject-specific slopes will be used to assess achievement of steady-state kinetics by week 6.

*Carryover effects*. Carryover effects are not expected, given the interval between outcome ascertainment in consecutive periods (at least 8 weeks) and the time course of dietary effects on BP and plasma lipids. Nonetheless, we cannot categorically dismiss the possibility that a small carryover effect could occur. All period

one treatments are free of potential carryover effects; hence, unbiased but inefficient profiles of treatment effects are available using only period one observations. Detection of carryover effects is facilitated by the detailed kinetic modeling described above. If carryover is found for any diet, it will be quantified, and then adjusted estimates of the dietary effects will be provided as secondary analyses. Special designs for the accommodation of carryover effects (Koch 1989; Peace 1990) present drawbacks (e.g., confinement of participants to longer periods with fewer treatments) that are considered undesirable given the low probability of carryover in this setting.

*Risk prediction equations*. The impact of the diets on overall cardiovascular risk (**Specific Aim 5**) will be assessed using prediction equations derived from prospective observational studies. Because of several methodologic issues [i.e., equations without relevant covariates (e.g., none with triglycerides); concerns about generalizability (e.g. most equations derived from populations of European Americans); uncertainties about the meaning of diet-induced reductions in HDL], these analyses will be considered exploratory. Still, an assessment of the overall impact of the diets on cardiovascular risk has strong conceptual appeal and obvious public health significance. Using available risk equations from the Framingham Heart Study (Wilson, 1998), from NHANES I and II (Liao, 1999), and from other cohorts (MRFIT, Pooling Project, ARIC), we will assess the overall effects of the diets on cardiovascular risk in our study population, in relevant subgroups, and, more broadly, to the US population. Presently, several health organizations in the US (e.g. AHA and NHLBI) and Europe are developing prediction models to estimate cardiovascular risk in diverse populations. Once these new equations become available, we will refine our plans and amend the protocol accordingly.

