Randomization (RZ: 0 – 7 days after end of run-in): Upon successful completion of run-in, eligible and interested participants are asked to sign an informed consent statement that covers the main portion of the trial (randomization and the subsequent 3 feeding periods). Participants are randomized to one of six sequences of the three diets (CARB, UNSAT, PROTEIN). Randomization is stratified by clinic. Participants are not told the sequence of diets to which they have been assigned. Except for staff involved in meal preparation, data collection personnel are blinded to diet sequence. As in the DASH and DASH-Sodium trials, each clinic operation is organized, in terms of space and personnel, to accomplish blinding of data collectors. Omni-Heart Protocol Version 1.00 October 1, 2003 Page 17

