For lipids, the minimum detectable effect sizes represent approximately 3% to 6% changes from expected mean concentrations (e.g. 140 mg/dl for LDL-C, 50 mg/dl for HDL-C, and 150 mg/dl for TG). For VLDL-apoB, the differences represent a 13% change from the mean (e.g. 12 mg/dl) for the full cohort and 20% for the n=80 subgroup. For VLDL-CIII, the differences represent a 10% change from the mean (e.g. 5 mg/dl) for the full cohort and a15% change for the n=80 subgroup. For fasting glucose, the differences represent 3 to 6% changes from typical mean values, e.g. 80 mg/dl. For fasting insulin and the insulin resistance index (HOMA), the differences represent changes of 20% and 8% from expected mean values of 5 uU/ml for insulin and 1.2 for HOMA (Mathews, 1985).

For the primary and secondary outcome variables, the standard deviation (SD) of change from beginning to end of the intervention periods in control subjects on the DASH trial were used to compute sample size requirements. These SDs were 6.4 mmHg for systolic BP, 4.8 mmHg for diastolic BP, 23 mg/dl for LDL-C, 5.4 mg/dl for HDL-C, 35 mg/dl for triglycerides, 7.6 mg/dl for fasting glucose, and 4.0 uU/ml for fasting insulin. The SDs for BP are based on means from clusters of 5 days of measurements. Because the eligibility criteria of the Omni-Heart and DASH trials are similar and because our recruitment strategies are likewise similar, these SDs are the most applicable. Still, the BP measurement technique of this trial (oscillometric) differs from that of the previous DASH trials (auscultatory); however, even if the actual SDs are slightly higher than projected, projected power should remain high, especially given the anticipated effect sizes (discussed below).

For the VLDL measurements, apoB and apo CIII, SDs of change are 6.1mg/dl and 2.0 mg/dl, respectively. These are based on the differences between baseline and 1 year in a random sample of 100 patients in the control group of the CARE trial ([name], unpublished). However, variability would be expected to be greater in free-living patients over 1 year than in our trial participants who eat in a controlled setting for 6 weeks. Hence, the minimum detectable differences derived from these SDs, while quite small, are likely to be greater than those actually detectable in this trial. For the insulin resistance HOMA index, the reproducibility data of Mathews (1985) was used, i.e. a CV of 31% (mean 1.2, SD 0.37).

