Randomization: Randomization assignments to one of six sequences of the 3 diets are generated by the data manager, after confirming, by computer program, that all screening activities have occurred, that the participant meets all eligibility criteria, and that all required baseline data have been collected. Diet sequences are stratified by site with varying block sizes to ensure a balance of sequences at each site.

Blinding: Until the end of the trial, all investigators, staff and participants are masked to trial outcome data, with the exception of the trial statisticians, the data manager, the NHLBI project officer, and the Data, Safety and Monitoring Committee. Due to the nature of the intervention, however, kitchen staff are unmasked to diet assignment. All BP observers are blinded to diet assignment, and participants are blinded to diet-specific, post-randomization BPs until the end of the trial. However, a mean of all readings, across diets, will be provided to the participant **at** the end of feeding.

Confidentiality: Each participant is assigned a unique study identification number. The data management and statistical unit do not have access to the list of participant names and ID numbers and therefore cannot link names to data. Files of study data include the study identification number but not participant names. Any hardcopy of data forms obtained by the coordinating unit (for example, as part of spot-checking for quality control) are maintained in locked file cabinets under the supervision of [name].

At the clinical centers, data are collected on forms with fields for study identification number but without a field for the participant's name. Still, lists of participant names, identification numbers, and contact information are used during the study to maintain contact with participants and eventually to provide feedback on study and personal results. All hardopies of forms are stored in locked file cabinets. All computer files are password protected. Participant results will only be released to the participant unless he/she provides written approval to release data (e.g. laboratory results to personal provider).

Data will be only be presented and published in aggregate, i.e. no identifying characteristics of participants will be published or presented.

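### The paired t-test named for the primary SBP contrast has no period term, so any common time trend in this three-period crossover would needlessly cost power

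*Protocol*

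**What the plan says.** Section 4.3.2 sets the design: "Participants are randomized to one of six sequences of the three diets (CARB, UNSAT, PROTEIN"). Section 9 adds that "Diet sequences are stratified by site with varying block sizes to ensure a balance of sequences at each site".

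Section 4.11 defines the primary outcomes as raw within-person differences between diets in end-of-period SBP and in week 6 LDL-C. Its rule for choosing a test is that "Inferential contrasts will be calculated using the simplest appropriate statistical method". The one method it names is for SBP, given as an example: "the equal-variances paired t-test of equal blood-pressure effects on two diets will likely be satisfactory". Mixed models have a secondary role: "Supplementary detailed modeling of the trajectory of repeatedly observed outcomes and its dependence on covariates will be conducted in the mixed effects models framework". The covariates are not listed. The remaining paragraphs of section 4.11 deal with steady state and carryover, and period is not named as a term in any analysis.

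Section 4.10 bases Table 5, for BP and the conventional lipids, on "the standard deviation (SD) of change from beginning to end of the intervention periods in control subjects on the DASH trial": 6.4 mmHg for SBP and 23 mg/dl for LDL-C.

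**The concern.** Within each participant, the difference between two diets is also a difference between two periods. Over six sequences that period difference takes both signs, and a pooled paired t-test counts its spread as random error. An SD of change is measured about the group's mean change, so a trend shared by everyone is absent from the planning SD but present in the error term of the named test.

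Participation covers 19 weeks of feeding plus two washouts of at least 2 weeks, so about 23 weeks or more, with BP measured throughout. Some common drift in BP or lipids is conceivable. If it occurs, the confidence intervals are wider than the design requires and power is lower than planned. The randomisation to six sequences already allows the trend to be removed, but the named test does not use it.

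**Working it through.** **Inputs.** From section 4.10: n = 160, two-sided alpha 0.05, SD of the paired difference 6.4 mmHg (SBP) and 23 mg/dl (LDL-C). From sections 4.3.2 and 9: six sequences, blocked within site, so close to equal in number. Assumption, because the protocol gives no figure: a linear period effect of d = 1, 2 or 3 mmHg per period, that is 2, 4 or 6 mmHg from period 1 to period 3.

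**Step 1: reproduce Table 5.** The minimum detectable difference (MDD) is (1.960 + z for power) × SD / √n.

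- SBP, 80% power: 2.802 × 6.4 / √160 = 1.42 (1.43 by noncentral t). Table 5 has 1.4.
- SBP, 90% power: 1.64 (1.65 by noncentral t). Table 5 has 1.7.
- LDL-C: 5.09 and 5.89 (5.13 and 5.93 by noncentral t). Table 5 has 5.1 and 5.9.

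Table 5 therefore reproduces as a paired comparison with no period effect.

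**Step 2: variance added by period.** For any two diets, the six sequences give period differences of +2d, +d, +d, −d, −d and −2d. Their mean is 0. Their mean square is (4 + 1 + 1 + 1 + 1 + 4)d² / 6 = 2d².

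**Step 3: what this does to the test.** With balanced sequences the period differences cancel from the mean. The true standard error stays at 6.4 / √160 = 0.506, and only the estimated one rises, to √(40.96 + 2d²) / √160. The test rejects when the mean difference exceeds c = 1.975 × the estimated SE (t on 159 df). Power at a true difference Δ is therefore close to Φ((Δ − c) / 0.506), and the 80% MDD is close to c + 0.842 × 0.506 = c + 0.426.

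| d (mmHg per period) | SD seen by the test | Estimated SE | c | Power at 1.42 mmHg | 80% MDD (mmHg) |
|---|---|---|---|---|---|
| 0 | 6.40 | 0.506 | 0.999 | 80% | 1.43 |
| 1 | 6.55 | 0.518 | 1.023 | 78% | 1.45 |
| 2 | 7.00 | 0.553 | 1.093 | 74% | 1.52 |
| 3 | 7.68 | 0.607 | 1.199 | 67% | 1.62 |

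Simulated trials of 160 participants agree with these powers to within about a percentage point. In simulation the type I error of the paired t-test falls to 0.046, 0.035 and 0.020 for d = 1, 2 and 3, and the estimate shows no bias.

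**Step 4: with period in the model.** Simulated power at 1.42 mmHg is 79–80% for all three drifts, with type I error of 0.051–0.052. The MDD is about 1.43 mmHg on 157 df, so the cost is negligible.

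**Step 5: LDL-C.** The same formulas with SD 23 give an 80% MDD of c + 0.842 × 1.818. For assumed steps of 2, 5 and 10 mg/dl per period this is 5.15, 5.29 and 5.75 mg/dl, against 5.12 with no drift. LDL-C is less sensitive because its SD is large relative to plausible drift.

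**Step 6: imbalance.** Section 4.11 drops incomplete pairs and analyses subgroups separately, while randomisation is stratified only by site. As an illustration, suppose 20% of participants due PROTEIN in the last period are lost. The mean period difference in PROTEIN minus CARB is then (0.8 × 3d − 3d) / 5.6 = −0.107d, about −0.2 mmHg at d = 2. This is small, and a period term removes it.

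**The case against.** The best defence is that the paired t-test is only an example for one outcome, qualified as likely to be satisfactory under a rule of the simplest appropriate method. The text does not rule out a period-adjusted analysis, and a separate statistical analysis plan might add one. That stands, and it limits the point to the method actually named.

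The second defence is that little would be lost. The error is conservative under balance. A step of 1 mmHg costs about 2 percentage points of power. Even at 3 mmHg per period, power exceeds 99.9% for the 3.2 mmHg SBP effect that section 4.10 cites as plausible for PROTEIN. Section 4.10 also accepts slightly higher SDs. Screening, run-in and weekly readings precede each endpoint and should reduce habituation. Overlapping waves loosen the link between period and season, so a period term would not remove all seasonal variation. Incomplete data were reported as very rare in the earlier DASH trials. All of this stands and keeps the point modest.

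Two stronger readings are tempting, and the protocol supports neither.

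- A reader might infer that Table 5 is not delivered. That would need a drift which the protocol neither states nor implies, and with no drift the table reproduces. Treating the added 2d² as real noise in the estimate would also overstate the loss, because under balance period effects cancel from the mean.
- A reader might infer from "unbiased but inefficient profiles of treatment effects are available using only period one observations" that carryover is handled with period-one data alone. Section 4.11 offers that as an available fallback. It also plans detection through the kinetic models and, if carryover is found, quantified and adjusted secondary estimates.

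**Conclusion.** The point holds as a matter of efficiency. The only primary method named leaves out a factor that the randomisation was built to separate, and Table 5 has no allowance for it. It is not a validity failure: with balanced sequences the estimate is unbiased and the type I error is at or below 5%.

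The size depends wholly on an unknown drift. At zero there is no loss, at 1 mmHg per period it is trivial, and from about 2 mmHg per period it becomes material: 74% power at 2 and 67% at 3, against 80% planned. These figures assume a linear trend, equal sequence numbers and the planning SD of 6.4 mmHg. A shift confined to period 1 adds only (2/3)d² and costs less. Any bias arises only where dropout or subgrouping unbalances the sequences, and it is likely to be small. The change is worth making because it costs almost nothing and protects against a trend whose size cannot be known in advance.

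**What to change.** Rewrite the analysis framework paragraph of section 4.11. Make the primary analysis of SBP, LDL-C and the other outcomes a linear mixed model with fixed effects for diet and period (and site, as the stratification factor) and a random participant effect. Take the three pairwise diet contrasts and their 95% confidence intervals from that model. Keep the paired t-test as a check, without the equal-variances qualifier, which has no meaning for a paired test. Use the same model within subgroups, where sequence balance is not assured.

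The cost is one paragraph and about 2 degrees of freedom. No new data are needed, and the sample size and Table 5 need not change.

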# 1. SUMMARY

While there is widespread consensus that the optimal diet to reduce cardiovascular risk should be low in saturated fat **and cholesterol**, the type of macronutrient that should replace saturated fat (carbohydrate, protein or unsaturated fat) is uncertain. The Omni-Heart trial evaluates the effects of these 3 macronutrients on established coronary risk factors and a selected group of emerging risk factors. The core design is a randomized, three period cross-over feeding study that compares the effects on blood pressure and plasma lipids of a carbohydrate-rich diet (CARB) to a diet rich in protein, predominantly plant-based protein, and another diet rich in unsaturated fat (UNSAT), predominantly monounsaturated fat. The CARB diet has been shown to reduce blood pressure and LDL-cholesterol substantially, and is currently recommended by policy makers. During a 1 week run-in, all participants are fed samples of the 3 study diets (CARB, PROTEIN and UNSAT). Using a three period cross-over design, participants are then randomly assigned to the CARB, PROTEIN OR UNSAT diet. Each feeding period lasts 6 weeks: a washout period of at least 2 weeks separates each feeding period. Throughout feeding (run-in and the 3 intervention periods), participants are fed sufficient calories to maintain their weight. Trial participants (n=160, ~ 50% female, ~ 50% African-American, ~30% hypertensive) are 30 years of age or older, with a blood pressure that is above optimal but less than stage 2 hypertension (systolic blood pressure of 120-159 mmHg or diastolic blood pressure of 80-99 mmHg). Primary outcomes variables are blood pressure and plasma lipid risk factors (LDL-C, HDL-C and triglycerides). Other outcomes are total cholesterol, apolipoproteins VLDL-apoB, VLDL-apoCIII, apolipoprotein B, non-HDL cholesterol, and lipoprotein(a).

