# 3.2.2 Effects of dietary fat by initial lipid level:

Dietary effects on plasma lipids may be influenced by baseline levels. It has been long assumed that cholesterol-lowering effects of diet are proportional to the initial level, based on studies of Keys (1957). However, evidence from experimental studies is sparse. In DASH, the initial level did not affect the extent of LDL reduction from the **reduced**-fat, carbohydrate-**rich** diet. This unexpected finding needs to be confirmed and extended to the effects of unsaturated fats and protein. As regards protein, Anderson et al (1995) reported in a meta-analysis that soy protein reduced cholesterol in hypercholesterolemic patients but only minimally in those with average cholesterol concentrations. This result is not fully convincing because the studies in hypercholesterolemic patients were not as well controlled as those in normocholesterolemics.

It has been only recently established that the triglyceride-lowering effects of the statin drugs, even when expressed as a percentage change, are directly proportional to the baseline triglyceride level (Stein 1998). It is considered a truism in the lipid field that the hypertriglyceridemic effect of dietary carbohydrate is increased in persons with higher triglyceride levels, although this has not been rigorously established in a controlled trial. Triglycerides are gaining increased importance as a risk factor in view of meta-analyses that demonstrate an independent prognostic effect (Hokanson and Austin, 1996). It is noteworthy that **OmniHeart** has sufficient power to compare effects in persons with triglyceride levels above vs below 150 mg/dl, a level recommended by NCEP-ATP-III as a cutpoint for defining a normal triglyceride.

Finally, the influence of baseline HDL needs to be investigated. Recently Azstalos (2000) reported that HDL reduction from a low-fat diet only occurs in patients with above-average baseline levels, a finding also observed in DASH (Obarzanek 2001). The influence of baseline lipid concentrations on the effects of dietary fat, carbohydrate and protein could have immense clinical implications and lead to dietary guidelines more tailored to the lipid phenotype of patients.

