## 4.2.1 Recruitment of minorities and women

Because of the disproportionate burden of hypertension and its complications in African-Americans and because of the BP responsiveness to dietary interventions in African-Americans, 50% is the trial recruitment goal for African-Americans. In subgroup analyses, African-Americans will be compared to non-African-Americans (whites and non-African-American minorities). We anticipate that over 50% of trial participants will be women and that approximately 30-40% will have Stage 1 hypertension. Using recruitment procedures similar to DASH and DASH-Sodium, these goals are readily achievable without targeted recruitment efforts. However, both centers are fully capable of implementing targeted recruitment efforts if there is a shortfall in recruitment of an important subgroup.

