#### 4.10 Sample size

Table 5 displays the minimum detectable, between-diet differences for primary, secondary and other outcome variables in the full cohort (n=160) and in subgroups (n=80 and 70) at powers of 80% and 90% (2sided alpha, p=0.05). The sample size of the trial (n=160) was selected because it provided adequate power to detect between-diet differences in our primary outcome variables that have public health significance, both overall and in subgroups. Specifically, the minimum detectable effect size for our primary outcomes, systolic BP and LDL-C, are < 3 mmHg and < 10 mg/dl, respectively, even in subgroups that comprise 40 % (n=64) of participants. For instance, Stamler (1989) has estimated that a population wide 3 mmHg reduction in systolic BP will lower coronary heart disease mortality by 5% and stroke mortality by 8%. Furthermore, the BP effect sizes are plausible based on extrapolations from the INTERSALT observational study (Stamler, 1996), i.e. a difference in total protein intake of 40 gm per day (a conservative estimate of the contrast in protein between CARB and PROTEIN) is associated with a 3.2 mmHg reduction in systolic BP and 2.6 mmHg reduction in diastolic BP. Likewise, the small trial by Ferrara (2000), which documented a 7 mmHg reduction in systolic BP and 6 mmHg reduction in diastolic BP from replacing saturated fat with olive oil, suggests that our trial is sufficiently powered to detect more modest BP reductions from UNSAT in our population with lower BP. If non-hypertensives comprise 70% of study participants, the minimum detectable between-diet difference in SBP and DBP at 80% power is 1.7 and 1.3 mmHg for non-hypertensives and 2.6 and 2.0 mmHg for hypertensives. Corresponding estimates at 90% power are 2.0 and 1.5 mmHg for nonhypertensives and 3.1 and 2.3 mmHg for hypertensives.

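### Section 3.2.2 claims power to compare triglyceride subgroups and Section 4.2.1 promises a race comparison, but Section 4.11 tests only within subgroups and Table 5 gives only within-group detectable differences

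*Protocol*

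**What the plan says.** Two passages speak of comparing subgroups. Section 3.2.2 says the trial "has sufficient power to compare effects in persons with triglyceride levels above vs below 150 mg/dl". Section 4.2.1 says: "In subgroup analyses, African-Americans will be compared to non-African-Americans".

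The method is in Section 4.11. Under the subgroup heading it reads "Analyses will be performed separately within subgroups" and lists gender, race-ethnicity, menopausal status, age, weight status and baseline level of the outcome. The multiple-comparisons paragraph sets unadjusted p<0.05 for each analysis. For continuous factors such as age, baseline BP and baseline lipids, Section 4.11 adds that an analysis of covariance may be more powerful, without committing to it.

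Power is in Section 4.10 and Table 5. They give minimum detectable differences between diets "in the full cohort (n=160) and in subgroups (n=80 and 70"), and Section 4.10 adds figures for hypertensives and non-hypertensives taken separately. None of these figures is for a difference between two subgroups.

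**The concern.** Whether a diet works in a subgroup and whether it works differently in two subgroups are separate questions. Section 3.2.2 asserts power for the second; the method and the power table address only the first. That section also says that dependence of diet effects on baseline lipids could lead to dietary guidelines tailored to lipid phenotype, which is a statement about effect modification.

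If the plan is followed as written, the natural way to report a comparison is to note that the effect reached p<0.05 in one subgroup and not in the other. That pattern can arise when the true effects are identical. A reader who takes Table 5's subgroup columns as support for Section 3.2.2 would also believe the trial can detect smaller subgroup contrasts than it can.

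**Working it through.** **Inputs, all from Section 4.10 unless noted**
- Power and alpha: "at powers of 80% and 90% (2sided alpha, p=0.05").
- SDs of change: "These SDs were 6.4 mmHg for systolic BP, 4.8 mmHg for diastolic BP, 23 mg/dl for LDL-C, 5.4 mg/dl for HDL-C, 35 mg/dl for triglycerides". Table 5 treats these as the SD of the within-person difference between two diets; the same is done here.
- Expected composition (Section 1): "n=160, ~ 50% female, ~ 50% African-American, ~30% hypertensive".
- Normal quantiles: 1.960 + 0.842 = 2.802 at 80% power; 1.960 + 1.282 = 3.242 at 90%.

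**Step 1. Reproduce Table 5 (80% power).** Within one group, MDD = 2.802 × SD / √n.

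| Outcome | n=160 | Table 5 | n=80 | Table 5 |
|---|---|---|---|---|
| SBP, mmHg | 2.802 × 6.4/12.65 = 1.42 | 1.4 | 2.802 × 6.4/8.944 = 2.00 | 2.0 |
| LDL-C, mg/dl | 5.09 | 5.1 | 7.20 (7.29 with the t distribution) | 7.3 |
| TG, mg/dl | 7.75 (7.80 with t) | 7.9 | 10.96 (11.10 with t) | 11.1 |

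Agreement is to within 0.1. The systolic figures for non-hypertensives (n=112: 1.69, stated 1.7) and hypertensives (n=48: 2.59, stated 2.6) reproduce in the same way. So all of these are paired calculations inside a single group.

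**Step 2. Detectable difference between two subgroups.** The quantity is the difference between two independent means of within-person diet differences: MDD = 2.802 × SD × √(1/n1 + 1/n2). For 80 and 80 the root is √0.025 = 0.1581.

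| Outcome | 80% power | 90% power | Full-cohort value, 80% (Step 1) |
|---|---|---|---|
| SBP, mmHg | 2.802 × 6.4 × 0.1581 = 2.84 | 3.28 | 1.42 |
| LDL-C, mg/dl | 2.802 × 23 × 0.1581 = 10.2 | 11.8 | 5.09 |
| TG, mg/dl | 2.802 × 35 × 0.1581 = 15.5 | 17.9 | 7.75 |

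The ratio to the full-cohort value is √0.025 × √160 = 2.00 whatever the SD, and an even split gives the smallest ratio. For the expected hypertension split (48 and 112) it is 2.18, or 3.09 mmHg for SBP.

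The protocol gives no share above 150 mg/dl for triglycerides. As assumptions:
- smaller group 50%: 15.5 mg/dl
- smaller group 30% (48/112): 2.802 × 35 × √(1/48 + 1/112) = 16.9 mg/dl
- smaller group 20% (32/128): 2.802 × 35 × √(1/32 + 1/128) = 19.4 mg/dl

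**Step 3. Power for a modest contrast.** For SBP with 80 and 80, the standard error is 6.4 × 0.1581 = 1.012. For a contrast of 1.4 mmHg, power = Φ(1.4/1.012 − 1.96) = Φ(−0.577) = 28%.

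**Step 4. How often separate tests disagree when the true effects are equal.** In one subgroup of 80 the standard error is 6.4/8.944 = 0.7155 and power is p = Φ(δ/0.7155 − 1.96). The chance that exactly one of two such subgroups is significant is 2p(1 − p).

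| True SBP effect in both | p | One significant, one not |
|---|---|---|
| 1.4 mmHg | 0.50 | 50% |
| 2.0 mmHg | 0.80 | 32% |
| 3.2 mmHg | 0.994 | 1% |

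Because 2p(1 − p) cannot exceed 0.5, the first row is the worst case for an even split. The 3.2 mmHg row uses the protein effect that Section 4.10 calls plausible.

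**The case against.** Much of the case on the other side stands.

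A reader might infer that the protocol claims power to compare subgroups throughout. It does not: the explicit claim is one sentence in the background, about triglycerides. For race, Section 4.2.1 states an intention to compare, with no power attached. Section 3.2.1 credits an earlier trial with power to detect race differences, but for this trial its wording is adequate power in subgroups.

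A reader might also think Section 4.10 is wrong to claim adequate power "both overall and in subgroups". The sentence is about differences between diets, and as a within-subgroup statement Step 1 supports it. Section 2.2 calls these analyses subsidiary and says the aims will be addressed in subgroups, so estimating the diet effect inside each subgroup is a legitimate objective.

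Nor can one conclude that no interaction test exists. The statistical analysis plan is not at hand and may contain one. Section 4.11 mentions analysis of covariance for continuous factors, which would cover baseline triglycerides, and supplementary mixed models that examine covariates. But the covariance analysis is optional and does not reach sex, race or menopausal status, and the mixed-model sentence names no diet-by-subgroup term.

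It would be too strong to say that separate testing misleads half the time: the rate depends on the true effect and is about 1% at 3.2 mmHg. Finally, the protocol sets no target for a subgroup contrast, so nothing in it shows that 15.5 mg/dl, about 10% of the assumed triglyceride mean of 150 mg/dl, is inadequate. What remains is that no calculation in the protocol supports the claim in Section 3.2.2, and the rule in Section 4.11 does not make the comparisons announced in Sections 3.2.2 and 4.2.1.

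**Conclusion.** The point holds as an internal mismatch. The protocol asserts power for a triglyceride subgroup comparison and announces a race comparison, but prescribes separate within-subgroup tests and supplies only within-group detectable differences. The contrast detectable between equal subgroups is twice the full-cohort value and 1.41 (√2) times the n=80 value in Step 1; unequal subgroups do worse.

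These sizes take the protocol's SDs as applying to the paired diet difference and as equal in both subgroups, with all 160 participants contributing. The factor of two does not depend on the value of the SD. The 30% and 20% triglyceride shares are assumptions. Since the analyses are subsidiary and Table 5 is correct for what it covers, this is a correction that should be made; it does not threaten the primary comparisons.

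**What to change.** In Section 4.11, for each pre-specified subgroup factor, add a test of diet-by-subgroup interaction that compares within-person diet differences between the subgroups. A two-sample t-test or a regression on the subgroup factor fits the paired t-test used for the primary outcomes; an interaction term in the supplementary mixed model is an alternative. State that within-subgroup estimates and confidence intervals are descriptive and that any claim of a subgroup difference rests on the interaction alone.

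In Section 3.2.2, either give the between-subgroup detectable difference for triglycerides, with the assumed share above 150 mg/dl, or limit the sentence to power within subgroups. The within-subgroup power statement in Section 4.10 needs no correction.

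The cost is wording only, with no added participants, visits or measurements. The stated power for comparing subgroups will look less favourable.
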